# PROTOCOL AMENDMENT SUMMARY OF CHANGES

This summary of changes document has been prepared to indicate the major changes made to Protocol ALXN1210-PNH-401, Amendment 3.0.

### Amendment 3 (07 May 2021)

This amendment is considered to be non-substantial based on the criteria set forth in Article 10(a) of Directive 2001/20/EC of the European Parliament and the Council of the European Union.

Other changes implemented through this Amendment constitute minor editorial corrections and fixing of inconsistencies.

#### **Overall Rationale for the Amendment:**

Section # and Name	Description of Change	Brief Rationale		
Section 1.1 Synopsis	Text regarding ravulizumab dosing language around home visits in Synopsis updated to match Section 4.1.	To clarify and make information consistent within the protocol.		
Section 1.3 Schedule of Activities Table 1	Note added to clarify that all study assessments for a given study day are to be completed on the same day. Additionally, note added to clarify that PD sampling is measurement of serum free C5 and total C5 concentration.	Added for clarity.		
Section 9.4.5 Prior and Concomitant Medication	Text updated to clarify use of medication 28 days prior to start of Screening.	To clarify and make information consistent within the protocol.		
Section 10.3 Appendix 3 Adverse Events: Definitions and Procedures for Recording, Evaluating, Follow-up, and Reporting	Deleted text pertaining to reporting of serious adverse events	Safety Reporting will not be done via the RAVE Electronic Safety Gateway in this study as RAVE Classic is being used, which does not have this feature.		
Section 10.7 COVID-19 Vaccine Risk Assessment	COVID-19 vaccines risk assessment language included.	Section newly added to provide potential risks identified and mitigation measures put in place in light of the COVID-19 vaccination rollout.		

The main rationale for this Amendment is to include COVID-19 vaccine risk assessment.

## 1. **PROTOCOL SUMMARY**

### 1.1. Synopsis

#### **Protocol Title:**

Phase 4, Single-Arm Study of Ravulizumab in Adult Participants with Paroxysmal Nocturnal Hemoglobinuria Currently Treated with High-Dose Eculizumab

#### **Short Title:**

Ravulizumab in Adult Participants with Paroxysmal Nocturnal Hemoglobinuria Currently Treated with High-Dose Eculizumab

### **Rationale:**

To assess the safety, efficacy, pharmacokinetics (PK), and pharmacodynamics (PD) of ravulizumab in participants who are prescribed and are receiving a higher than approved dose of Soliris® (eculizumab) to treat paroxysmal nocturnal hemoglobinuria (PNH)

### **Objectives and Endpoints**

Objectives	Endpoints				

 
Primary
 
To evaluate the prevalence of free complement component 5 (C5)-associated breakthrough hemolysis (BTH) in participants on high-dose eculizumab who switch to ravulizumab (per approved dose regimen)
 
	• Proportion of participants who experience free C5- associated BTH through Day 351. Free C5- associated BTH is defined as BTH concurrent with free C5 concentrations $\geq 0.5 \ \mu g/mL$ . BTH is defined as at least one new or worsening symptom or sign of intravascular hemolysis (fatigue, hemoglobinuria, abdominal pain, shortness of breath [dyspnea], anemia [hemoglobin < 10 g/dL], MAVE, including thrombosis, dysphagia, or erectile dysfunction) in the presence of elevated LDH $\geq 2 \times ULN$ .				

 
Secondary
 
To evaluate efficacy by other measures in participants on high-dose eculizumab who switch to ravulizumab
 
	
 
Proportion of participants who experience BTH through Day 351
 
Hemolysis as directly measured by LDH-PCHG from baseline to Day 351
 
Proportion of participants who receive a transfusion, from baseline to Day 351
 
Proportion of participants with stabilized hemoglobin, defined as avoidance of a ≥ 2 g/dL decrease in hemoglobin level from baseline in the absence of transfusion from baseline to Day 351
 
				

Objectives	Endpoints			
Exploratory				
To evaluate Patient-Reported Outcomes over time for those who switch to Ravulizumab from high-dose	
 
Patient-reported PNH Symptoms (PRS) at baseline, Day 183 and Day 351
 
			
eculizumab	• Healthcare Resource Utilization (HRU) at baseline, Day 183 and Day 351			
Safety				
• To evaluate the safety and tolerability of ravulizumab in participants on high-dose eculizumab who switch to ravulizumab	• Physical examinations, vital signs, and laboratory assessment results, and incidence of adverse events (AEs) and serious adverse events (SAEs)			
	• Proportion of participants who develop (ravulizumab) antidrug antibodies (ADAs)			
PK/PD				
• To characterize the PK/PD of ravulizumab in participants on high-dose eculizumab who switch to	• Change in serum ravulizumab concentration over time			
ravulızumab	• Change in serum free and total C5 concentrations over time			

Abbreviations: ADA = antidrug antibody; AE – adverse event; BTH = breakthrough hemolysis; C5 = complement component C5; LDH-PCHG = lactate dehydrogenase percent change; MAVE = major adverse vascular event; PD = pharmacodynamic; PK = pharmacokinetic; SAE = serious adverse event

### **Overall Design**

This is a Phase 4, single-arm, open-label study to evaluate the efficacy and safety of ravulizumab in adult participants with PNH who switch from eculizumab 1200 mg every 2 weeks (q2w; ie, above the recommended dose) to ravulizumab (at the recommended dose).

The study will consist of a Screening Period of approximately 3 months and a Treatment Period of 351 days. All participants must provide informed consent prior to any procedures at the first Screening visit. All participants must have been prescribed and are receiving a stable dose of eculizumab 1200 mg q2w for at least 3 months prior to screening. During Screening, eculizumab may be administered at the participant's home at the discretion of the Investigator. During screening, participants will continue to receive eculizumab 1200 mg q2w, and blood samples will be collected for PD parameters and lactate dehydrogenase (LDH) levels.

Eligible participants will receive a loading dose of ravulizumab on Day 1, followed by maintenance doses on Day 15 and every 8 weeks (q8w), administered by intravenous (IV) infusion. Ravulizumab loading and maintenance doses will be based on participants' body weight per approved dose regimen. Ravulizumab dosing will be administered in the clinic by a trained member of the site study team; patients may have the option to receive study drug remotely at a medical facility that is located near the patient's home or at the patient's home by a qualified healthcare personnel.

The schedule of study visits and assessments is shown in Section 1.3.

An interim analysis will be performed on Day 183.

**Disclosure Statement:** This is a single-arm, open-label study.

#### Number of Participants:

Approximately 20 participants will be enrolled.

#### **Treatment Groups and Duration:**

This single-arm study will consist of a 3-month Screening Period and a 351-day Treatment Period. All eligible participants will receive ravulizumab according to approved dose regimen during the Treatment Period.

#### **Data Monitoring Committee: No**

#### 1.2. Schema

- a. Ravulizumab loading dose is 2400 mg for patients weighing ≥ 40 to < 60 kg, 2700 mg for patients weighing ≥ 60 to < 100 kg, or 3000 for participants weighing ≥ 100 kg.
- b. Ravulizumab maintenance dose is 3000 mg for patients weighing ≥ 40 to < 60 kg, 3300 mg for patients weighing ≥ 60 to < 100 kg, or 3600 mg for participants weighing ≥ 100 kg.

### **1.3.** Schedules of Activities

#### Table 1: Schedule of Study Visits and Assessments: Screening Visit Through Confirmation Visit

Period			Scr	eening			Notes		
Study Day	-85	-71	-57	-43	-29	-15			
Window (day)	± 2	± 2	± 2	± 2	± 2	± 2	All study assessments for a given Study Day must be completed on the same day as the study visit. The window of $\pm 2$ days is relative to Day 1 and allows for the Study Visit to occur $\pm 2$ days from the indicated study day		
Informed consent	Х								
Inclusion and exclusion criteria	Х								
Confirmation of meningococcal vaccination				Х			Refer to Section 6.5.1 for details		
Abbreviated physical examination	Х		Х		Х		Refer to Section 8.2.1 for details		
Height	Х								
Weight	Х		Х		X				
Medical history including PNH and eculizumab dosing history	Х								
Serum or urine pregnancy test	Х		Х		Х		Refer to Section 8.3.5 for details. Serum pregnancy test at Day -85, Urine pregnancy test at all other visits		
HIV testing	Х								
Chemistry including LDH	Х		Х		Х		Sample to be collected within 24 hours of or immediately prior to a scheduled dose of study drug (trough) and not from a heparinized line.		
Hematology including free hemoglobin and coagulation	Х		Х		Х		Blood will be collected predose and not from a heparinized line.		
Urinalysis and urine chemistry	Х		Х		X		Urine will be collected predose on dosing days.		
Safety 12-lead ECG	Х						Participants must be supine for approximately 5 to 10 minutes before ECG collection and remain supine but awake during ECG collection. Refer to Section 8.2.3 for details		
Vital signs	Х		Х		Х		Will be measured after the participant has been resting for at least 5 minutes. Refer to Section 8.2.2 for details		
PNH clone size	Х						WBC (granulocyte and monocyte) and RBC clone size measured by high-sensitivity flow cytometry at Screening; RBC clone size only at Screening		
Record transfusions and transfusion parameters	X	X	Х	Х	Х	Х	Transfusions given during and between visits will be recorded. This can be optionally performed by a phone call on Days -71, -43, and -15		

Period			Scre	ening			Notes		
Study Day	-85	-71	-57	-43	-29	-15			
Window (day)	± 2	± 2	± 2	± 2	± 2	± 2	All study assessments for a given Study Day must be completed on the same day as the study visit. The window of $\pm 2$ days is relative to Day 1 and allows for the Study Visit to occur $\pm 2$ days from the indicated study day		
PNH symptomatology	Х	Х	Х	Х	Х	Х	Investigator assessed and reported. Refer to Section 8.1.3 for details. This can be optionally performed by a phone call on Days -71, -43, and -15		
PD sampling			Х		Х		PD sampling is measurement of serum free C5 and total C5 concentration. Refer to Sections 8.5 and 8.6 for details		
Review safety card	Х	Х	Х	Х	Х	Х			
BTH	←Monitor continuously→			If a BTH event occurs during the Screening Period, the participant will be ineligible for the study. To confirm BTH, LDH, PK, and PD samples will be collected and analyzed. If the suspected event of BTH does not occur at a scheduled visit, an unscheduled visit should occur for evaluation of the participant and collection of the required LDH, PK, and PD samples.					
Concomitant medications		+	-Monitor c	ontinuously	$\rightarrow$				
Adverse events		÷	-Monitor c	ontinuously	$\rightarrow$				
Confirmation of eculizumab dose	X	X	X	X	X	Х	At the Investigator's discretion and preference of the patient, eculizumab may be administered at the participant's home (except at Visits -57 and -29) by a trained qualified staff member (Section 8)		

#### Table 1: Schedule of Study Visits and Assessments: Screening Visit Through Confirmation Visit

Abbreviations: ADA = antidrug antibody; AE = adverse event; BTH = breakthrough hemolysis; C5 = complement component C5; ECG = electrocardiogram; HIV = human immunodeficiency virus; LDH = lactate dehydrogenase; LDH-PCHG = lactate dehydrogenase percent change; PD = pharmacodynamic; PK = pharmacokinetic; RBC = red blood cell; SAE = serious adverse event; WBC = white blood cell.

Period	Confirmation Visit			Evalu	uation	Period			Unscheduled Visits	Follow- up call	Notes
Study Day	1	15	71	127	183	239	295	351/ ET	NA	407	
Window (day)	NA	± 2	±7	± 7	± 7	± 7	± 7	± 7		± 7	
Inclusion and exclusion criteria	Х										LDH and hematologic criteria assessed
Physical examination	Х							X			
Abbreviated physical examination		X	X	Х	Х	X	Х		Х		Refer to Section 8.2.1 for details
Weight	Х	Х	Х	Х	Х	Х	Х	Х	Х		
Serum or urine pregnancy test	Х	X	X	X	X	X	X	X	Х		Refer to Section 8.3.5 for details. Serum pregnancy test at Day 1, and Day 351/ET.; Urine pregnancy test at all other visits
Chemistry including LDH	Х	X	X	X	Х	X	Х	X	Х		Sample to be collected within 24 hours of or immediately prior to a scheduled dose of study drug (trough) and not from a heparinized line.
Hematology including free hemoglobin and coagulation	Х	X	X	Х	Х	X	Х	X	Х		Blood will be collected predose on dosing days and not from a heparinized line.
Urinalysis and urine chemistry	Х	Х	X	X	X	X	X	X	Х		Urine will be collected predose on dosing days.
Safety 12-lead ECG								X			Refer to Section 8.2.3 for details
Vital signs	Х	X	Х	Х	Х	X	Х	X	Х		Will be measured after the participant has been resting for at least 5 minutes. Refer to Section 8.2.2 for details
PNH clone size	Х			X				X			WBC (granulocyte and monocyte) and RBC clone size measured by high- sensitivity flow cytometry at Day 1; RBC clone size only at Day 127 and Day 351/ET

### Table 2: Schedule of Study Visits and Assessments: Confirmation Visit Through Follow-up

Period	Confirmation Visit			Eval	uation	Period			Unscheduled Visits	Follow- up call	Notes
Study Day	1	15	71	127	183	239	295	351/ ET	NA	407	
Window (day)	NA	± 2	±7	± 7	± 7	± 7	± 7	± 7		± 7	
PRS and HRU	X				X			X			Questionnaires at the confirmation visit administered prior to first dosing of Ravulizumab. PRS completed by the participant Refer to Section 8.10 for details
Record transfusions and transfusion parameters	Х	X	Х	Х	Х	Х	Х	Х	X		Transfusions given during and between visits will be recorded
PNH symptomatology	Х	X	X	X	X	X	X	X	Х		Investigator assessed and reported Refer to Section 8.1.3 for details
PK/PD sampling	Х	X	X	X	X			X	Х		Refer to Section 8.5 and Section 8.6 for details
Immunogenicity (ADA)	Х		X		X			X	Х		Samples will be collected predose
Review safety card	Х	Х	X	X	Х	X	X	Х	Х		
BTH				If a suspected event of BTH occurs, LDH, PK, and PD samples will be collected and analyzed . If the suspected event of BTH does not occur at a scheduled visit, an unscheduled visit should occur for evaluation of the participant and collection of the required LDH, PK, and PD samples.							
Concomitant medications				<del>(</del>	-Monito	r continu	ously→			•	
Adverse events				+	-Monito	r continu	ously→				

### Table 2: Schedule of Study Visits and Assessments: Confirmation Visit Through Follow-up

Period	Confirmation Visit		Evaluation Period			Unscheduled Follow- Visits up call	Notes				
Study Day	1	15	71	127	183	239	295	351/ ET	NA	407	
Window (day)	NA	± 2	± 7	± 7	± 7	± 7	± 7	± 7		± 7	
Ravulizumab administration	X	X	X	X	x	x	X		X		The dose of ravulizumab is based on the participant's last recorded study visit body weight as per approved dose regimen. Refer to Section 6.1.1 At the Investigator's discretion and in accordance with the local regulations, ravulizumab may be administered at the patient's home or at a medical facility close to the patient's home by a qualified healthcare personnel (see Section 8.11).

#### Table 2: Schedule of Study Visits and Assessments: Confirmation Visit Through Follow-up

Abbreviations: ADA = antidrug antibody; AE = adverse event; BTH = breakthrough hemolysis; C5 = complement component C5; ECG = electrocardiogram; ET = early termination; LDH = lactate dehydrogenase; LDH-PCHG = lactate dehydrogenase percent change; NA = not applicable; PD = pharmacodynamic; PK = pharmacokinetic; RBC = red blood cell; SAE = serious adverse event; WBC = white blood cell.

	Starting Visit	Example Visit	EOS/ET	Unscheduled visit	Follow- up call	Notes
Study Day	q6w Day 1	q6w Day 43	Day XX	NA	EOS/ET + 56 days	All subsequent q6w visits up to EOS/ET to follow the assessments shown in the example visit
Window (day)	NA	± 7	± 7		± 7	
Physical examination			Х			
Abbreviated physical examination	Х	Х		Х		Refer to Section 8.2.1 for details
Weight	Х	Х	Х	Х		
Serum or urine pregnancy test	Х	Х	X	Х		Refer to Section 8.3.5 for details
Chemistry including LDH	Х	X	X	Х		Sample to be collected within 24 hours of or immediately prior to a scheduled dose of study drug (trough) and not from a heparinized line.
Hematology including free hemoglobin and coagulation	Х	X	X	X		Blood will be collected predose on dosing days and not from a heparinized line.
Urinalysis and urine chemistry	Х	Х	Х	Х		Urine will be collected predose on dosing days.
Safety 12-lead ECG	Х		Х			Refer to Section 8.2.3 for details
Vital signs	Х	Х	Х	Х	Will be measured after the participant has been resting for 5 minutes. Refer to Section 8.2.2 for details	
PNH clone size	Х	X	X			WBC (granulocyte and monocyte) and RBC clone size measured by high-sensitivity flow cytometry at Day 1; RBC clone size only at Day 127 and Day 351/ET
Record transfusions and transfusion parameters	Х	Х	X	X		Transfusions given during and between visits will be recorded
PNH symptomatology	Х	X	X	X		Investigator assessed and reported. Refer to Section 8.1.3 for details
PK/PD sampling	Х	Х	Х	Х		Refer to Section 8.5 and Section 8.6 for details

### Table 3:Schedule of Study Visits and Assessments: q6w Dosing

	Starting Visit	Example Visit	EOS/ET	Unscheduled visit	Follow- Notes up call		
Study Day	q6w Day 1	q6w Day 43	Day XX	NA EOS/ET + 56 days		All subsequent q6w visits up to EOS/ET to follow the assessments shown in the example visit	
Window (day)	NA	±7	± 7		± 7		
Immunogenicity (ADA)	Х	Х	X	Х		Samples will be collected predose	
Review safety card	Х	Х	Х	Х			
BTH		←Monitor o	continuously→	under .		If a suspected event of BTH occurs, LDH, PK, and PD samples will be collected and analyzed. If the suspected event of BTH does not occur at a scheduled visit, an unscheduled visit should occur for evaluation of the participant and collection of the required LDH, PK, and PD samples.	
medications		~_lv	ionitor continuc	busiy→			
Adverse events		←N	Ionitor continue	ously→			
Ravulizumab administration	X	X		X		The dose of ravulizumab is based on the participant's last recorded study visit body weight as per approved dose regimen. Refer to Section 6.1.1 At the Investigator's discretion and in accordance with the local regulations, ravulizumab may be administered at the patient's home or at a medical facility close to the patient's home by a qualified healthcare personnel (see Section 8.11)	

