### 6.6.2. Permitted Change in Dosing Interval

If a participant experiences a free C5-related BTH during maintenance treatment with ravulizumab, shortening the dosing interval to every 6 weeks (q6w) is permitted at the discretion of the Investigator after discussion with Alexion's Medical Monitor. For these participants, the assessments performed at the first q6w visit would be those indicated in the SoA (Section 1.3). Subsequent q6w visit assessments would continue to be aligned to the example visit illustrated in Table 3, with the EOS/ET visit being on/after Day 351. Between the SoA-specified visits occurring at 6-week dosing frequency and the EOS/ET visit, any additional visits are to be classified as unscheduled visits and would follow the study procedures for unscheduled visits (Table 3).

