# 8.10. Patient-Reported Symptoms and Health Resource Utilization questionnaires

Patient-reported PNH symptoms (PRS) and Health Resource Utilization (HRU) data, will be collected at Day 1 (baseline), Day 183 and Day 351/ET in the eCRF by the Investigator and study-site personnel for all participants throughout the study. Protocol-mandated procedures, tests, and encounters are excluded.

For PRS, each participant will record the presence or absence of the signs and symptoms of PNH: fatigue, chest pain, abdominal pain, dyspnea, dysphagia, headache, confusion, erectile dysfunction (if applicable), discoloration of urine, discoloration of eyes (see Appendix 10.5.1).

For HRU, the Investigator or designee will record for each participant the number of clinic visits, emergency services utilized, hospitalization, missed work and also record the number of times the participant had darkened urine (see Appendix 10.5.2).

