# 9. STATISTICAL CONSIDERATIONS

# 9.1. Statistical Hypotheses

This is an estimation study; no formal statistical hypotheses will be tested.

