# 9.2. Sample Size Determination

The proposed sample size for this estimation study is approximately 20 participants. The range of possible proportions of participants experiencing free C5-associated BTH during the Treatment Period (with 95% exact confidence intervals) is as follows:

Proportion of BTH (participants with BTH/total population)	95% CI
95% (19/20)	75%, 100%
75% (15/20)	51%, 91%
50% (10/20)	27%, 73%
25% (5/20)	9%, 49%
10% (2/20)	1%, 32%
5% (1/20)	0%, 25%
0% (0/20)	0%, 17%

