8.3. Exploratory Endpoints and Analyses

8.3.1. Patient-Reported PNH symptoms

For PRS, each participant will record the presence or absence of the following signs and symptoms of PNH at baseline, Day 183, and Day 351/ET: fatigue, chest pain, abdominal pain, dyspnea, dysphagia, headache, confusion, erectile dysfunction (if applicable), discoloration of urine, and discoloration of eyes.

PRS data will be summarized descriptively by visit for the FAS. The summaries will include the proportion of participants affected by PNH symptoms, the frequency and severity of those symptoms, and the level of distress the symptoms caused.

All data will be listed.

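### The q6w schedule (Protocol Table 3) leaves out the PRS and HRU questionnaires that Section 8.10 requires from all participants, so any forms lost this way would come only from participants who had a free C5-related BTH

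*Protocol*

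**What the plan says.** **Schedule before any switch.** Protocol Table 2 has a PRS and HRU row marked at Day 1, Day 183 and Day 351/ET. Its note adds "Questionnaires at the confirmation visit administered prior to first dosing of Ravulizumab".

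**Protocol body.** Section 8.10 states that both questionnaires "will be collected at Day 1 (baseline), Day 183 and Day 351/ET in the eCRF by the Investigator and study-site personnel for all participants". It makes no exception for q6w.

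**Schedule after a switch.** Section 6.6.2 permits q6w, at the Investigator's discretion and after discussion with the Medical Monitor, for a participant with a free C5-related BTH on maintenance treatment. It continues: "Subsequent q6w visit assessments would continue to be aligned to the example visit illustrated in Table 3". Any extra visit before EOS/ET counts as unscheduled and follows the unscheduled column of Table 3. The note in Table 3 itself reads "All subsequent q6w visits up to EOS/ET to follow the assessments shown in the example visit". No column of Table 3 (starting visit, example visit, EOS/ET, unscheduled) lists PRS or HRU.

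**Analysis.** SAP Section 8.3.1 has each participant complete PRS at baseline, Day 183 and Day 351/ET, and says "PRS data will be summarized descriptively by visit for the FAS". SAP Section 8.3.2 treats HRU the same way. SAP Section 6.3.1 rules out imputation of efficacy data. SAP Section 16.2.5.2 bases percentages, by default, on participants who have an observation, and adds an Unknown or Missing category.

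**The concern.** The schedule that a site works from after a q6w switch disagrees with the section that defines the questionnaires. Section 8 of the Protocol treats adherence to the schedule of activities as mandatory. A coordinator who does exactly what Table 3 says would not hand out PRS or HRU again, even at an unscheduled visit near Day 183.

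The gap is not spread at random over the sample. The only route to Table 3 runs through a free C5-related BTH, which is the event counted in the primary endpoint. Section 2.1 gives the study's purpose as showing that the change of drug leaves the benefit/risk profile unaltered. Participants who broke through are therefore the ones whose later symptoms, hospital use and missed work a reader most wants to see. PRS asks about the past week and HRU about the past month, so a form missed at the time cannot be recovered later.

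**Working it through.** **1. Base.** The size of the analysis set comes from Protocol Section 9.2: "The proposed sample size for this estimation study is approximately 20 participants". Its exact 95% intervals reproduce in all seven rows. For example, the upper limit for 0/20 is 1 − 0.025^(1/20) = 16.84%, printed as 17%, and 5/20 gives 8.66% to 49.10%, printed as 9% and 49%. The present point does not depend on them; they only confirm 20 as the denominator.

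**2. The two schedules.** In Table 2 the PRS/HRU row stands between PNH clone size and transfusions. In Table 3 those two rows are adjacent and nothing stands between them.

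**3. Which forms are exposed.**

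| Participant | Day 1 | Day 183 | Day 351/ET |
|---|---|---|---|
| Stays on q8w | Table 2 | Table 2 | Table 2 |
| Switches after Day 183 | already collected | already collected | no prompt in Table 3 |
| Switches before Day 183 | already collected | no prompt in Table 3 | no prompt in Table 3 |

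Day 1 is never at risk, because that form precedes the first ravulizumab dose.

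**4. Calendar.** The q6w visits fall on s + 42i, where s is the q6w start day (assumed here, not given). The SAP window for Day 183 is Days 155–210.

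- s = 71: Days 113, 155, 197 and so on. Days 155 and 197 lie outside 183 ± 7 (Days 176–190) but inside the SAP window.
- s = 127: Days 169 and 211. Day 169 is inside the SAP window.
- In general the window covers 210 − 155 + 1 = 56 days, longer than the 42-day spacing. Anyone who switches before Day 183 therefore has at least one q6w visit in it, counting the starting visit.

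Section 6.6.2 places EOS on or after Day 351. If EOS is put on the 42-day grid, the first such visit is:

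- s = 57: 57 + 7×42 = 351
- s = 71: 71 + 7×42 = 365
- s = 127: 127 + 6×42 = 379

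The SAP window for Day 351 ends at Day 378, and Day 379 onward is labelled Follow-up. In the last case a completed EOS form would miss the Day 351 summary.

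**5. Possible size.** Let k of 20 participants be switchers without a form, and let p_n and p_s be the symptom prevalence in non-switchers and switchers.

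- Reported = p_n
- Full set = [(20 − k)·p_n + k·p_s]/20
- Reported − full = k·(p_n − p_s)/20, so the shift cannot exceed k/20 in either direction: 5, 10 or 25 points for k = 1, 2 or 5.

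The documents give none of k, p_n or p_s. With p_n assumed at 30%:

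| k | Reported | Full set, p_s = 80% to 100% | Full set, p_s = 30% |
|---|---|---|---|
| 1 | 30% | 32.5% to 33.5% | 30% |
| 2 | 30% | 35% to 37% | 30% |
| 5 | 30% | 42.5% to 47.5% | 30% |

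If switchers had recovered fully (p_s = 0, k = 2), the full value would be 18 × 0.30/20 = 27%, and the reported 30% would err against ravulizumab.

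For the Day 183 interim analysis of the first 10 participants (SAP Section 13), the same bound is k/10.

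**The case against.** A reader might infer that switchers drop out of the patient-reported analysis and that the results are therefore biased in favour of ravulizumab. The documents do not support that.

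- **No exclusion.** Section 8.10 and SAP Section 8.3 still require the forms from everyone. The FAS includes every dosed participant, and no rule removes switchers. Loss is a risk that arises if sites follow the table and not the text.
- **Not every form.** Nor does each switch take 5% out of the whole data set. Day 1 is always in hand, and so is Day 183 for anyone who switches later.
- **Not every breakthrough.** Switching is discretionary. A participant with a free C5-related BTH who stays on q8w remains on Table 2.
- **Direction unknown.** With recall of a week and a month, the episode behind the switch may have resolved by the questionnaire date.
- **Timing is largely handled.** SAP Section 6.4 assigns q6w records to analysis windows, so off-grid visits around Day 183 are not a separate defect.
- **Low stakes.** The endpoints are exploratory and descriptive in a study where "This is an estimation study; no formal statistical hypotheses will be tested". The SAP would show a Missing category and the number of switchers. Investigator-assessed PNH symptoms continue at every q6w visit.

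All of this stands and limits the point. It does not remove the contradiction between Table 3 and Section 8.10. Window mapping can place only records that exist, a Missing category shows a gap without filling it, and investigator-assessed symptoms replace neither the participant's own report nor resource use.

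**Conclusion.** The point holds as an inconsistency with a selective consequence. Table 3 omits PRS and HRU at every visit, against Section 8.10 and SAP Section 8.3. If sites follow Table 3 literally, the missing Day 351 forms, and the missing Day 183 forms of earlier switchers, would come only from participants with a free C5-related BTH. With no imputation and observed-only denominators, the summaries could then favour ravulizumab.

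That rests on two assumptions: that sites work from the table, and that switchers differ from the rest at the questionnaire date. The documents establish neither, so no size or direction can be claimed beyond the bound of k/20. No primary or secondary result changes. The correction is still worth making, because it is nearly free and the lost data could not be recovered.

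**What to change.** 1. **Protocol Table 3.** Add a PRS and HRU row, marked at EOS/ET and, for participants who switch before Day 183, at the q6w visit nearest Day 183 (starting visit included) within the SAP window of Days 155–210. Table 3 then agrees with Section 8.10.
2. **SAP Section 6.4.** State that the PRS and HRU forms from the q6w EOS visit are assigned to the Day 351 analysis visit even when that visit falls on or after Day 379.
3. **SAP Section 8.3.** Report PRS and HRU completion at Day 183 and Day 351 by q6w-switch status, so that a reader can see how many forms are missing and from whom.

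The cost is one table row, carried in a protocol amendment, and two SAP sentences. The forms are already required and the visits already planned, so no visit is added. For participants already past these visits, only items 2 and 3 can still help.
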